## Proposal:

1) Protocol Title: Cultivating Resilient and Strong Opinion Leaders (CRiSOL) Program

## 2) IRB Review History:

Considering that our initial exit interview was design to ask about a 1-year intervention focus on a different topic, we are submitting a more complete instrument that focuses on COVID-19. Finally, we are requesting to add a new member to our study.

Past modifications have been made to reflect COVID-19 recommendations. We requested a modification to our protocol to hold our biweekly intervention sessions via Zoom and to extend data collection efforts to on online or phone format in order to minimize spread of the virus. To reflect these changes we also requested changes to our dispersal of incentives, to allow for alternative modalities that do not require meeting face to face with participants. In June, we submitted a modification to expand the outreach in the community for 3 more months (until end of September 2020). We requested a modification to extend our project for a second year and submitted all necessary materials.

# 3) Objectives:

The purpose of this study is to implement an additional module related to COVID-19 to our pilot peer-driven intervention that seeks to address a cluster of health issues that have been shown to impact Latino immigrant communities. These health problems include Substance Abuse, Violence exposure, HIV/AIDS, and Mental Health (SAVAME). These conditions represent a syndemic because they act synergistically, and stem from multiple, common social and environmental determinants. The Cultivating Resilient and Strong Opinion Leaders (CRiSOL) intervention aims to reduce the impact of the SAVAME syndemic and COVID-19 among Latino immigrants in Philadelphia by integrating a community resilience and opinion leader framework.

The specific aims of the pilot study are:

- 1. To adapt and integrate two interventions previously implemented by our community partners in order to develop a new intervention to reduce the impact of the SAVAME syndemic among Latino immigrants in Philadelphia, with emphasis on changing social norms, promoting utilization of SAVAME-related health, behavioral, and social services, and promotion of individual and community resilience.
- 2. To recruit and train a small sample of peer leaders and implement the Creating Resilient and Strong Opinion Leaders (CRiSOL) pilot intervention in Philadelphia communities where Latino communities concentrate.
- 3. To test the pilot intervention using a comprehensive evaluation framework to generate feasibility, acceptability, and pilot efficacy data that will inform a future R01 application proposing an effectiveness trial of this intervention.
- 4. Include an additional 16-hour module related to COVID-19 to our previous implemented pilot.

#### 4) Background:

Project CRiSOL will incorporate resilience training with an established peer-driven intervention framework in an effort to address the health disparities that exist among Latino immigrants. CRiSOL focuses on a set of four inter-related syndemic conditions among Latinos: substance abuse, HIV, domestic violence and mental health. During the second year, we will focus on COVID-19.

This project focuses on Latinos, the nation's largest racial/ethnic minority group in the U.S. due to the mitigating social factors that they experience: 1 in 3 adults has not completed high school, 1 in 4 lives in poverty,  1 in 4 is uninsured,  and half experience discrimination and prejudice.  These social disadvantages result in health disparities, including a disproportionate impact of HIV, substance abuse, mental health problems, violence; and most recently, COVID-19.

Latinos represent 17% of the U.S. population but they make 21% of new HIV infections and have a diagnosis rate 3 times that of non-Hispanic Whites (NHW). Latinos are also diagnosed later and have lower rates of viral suppression than their NHW counterparts. The disparities extend to other STIs. For example, rates of chlamydia, gonorrhea, and syphilis are 1.8-2.2 times higher for Latinos compared to NHW.

Alcohol and substance abuse levels among Latinos are comparable to or greater than in other groups, but there are notable disparities in access, quality of care, and adherence to substance treatment among Latinos, calling for evidence- based and culturally responsive strategies to minimize these disparities.

About 28% of Latino men and 30% of Latinas will develop a psychiatric disorder over their lifetime. Latinos have the second highest rate of severe depression, the highest rate of moderate depression, and more signs of anxiety than other groups. Yet, this group is less likely to seek mental health care and shows lower rates of anti-depressants or anxiety- reducing medication utilization compared to NHW. 26

Latinos also experience a greater burden of violent victimization compared to NHW. Although levels of intimate partner violence (IPV) do not differ much between Latinos and other groups, socio-economic conditions, cultural beliefs, and immigration-related factors perpetuate and exacerbate the impact of IPV among Latinas.

This study focuses specifically on immigrants because migration is a social determinant of health. About 48.7% of Latino adults in the U.S. were born in another country, representing a particularly vulnerable population who faces additional disparaging barriers to health and health care, including poorer working conditions, acculturative stress, and discrimination. For 9 million Latino immigrants, undocumented status further limits access to services, education and work opportunities.

HIV, substance use, violence, and mental health have an even greater impact on Latino immigrants. Immigrants account for 43% of new HIV diagnoses in Latinos, are at increased risk of delayed HIV diagnosis and late presentation to care, and have shorter survival compared

to non-immigrant Latinos. Studies, including some by our own team, have shown high rates of STIs, sexual risk behavior, and substance abuse, among Latino immigrant samples and indicated a negative impact of migration to the U.S. on these behaviors. Cumulative exposure to U.S. society and higher acculturation increase the risk for substance use and psychiatric disorders. Immigrant women experience higher rates of IPV and are less likely to seek services than native populations.

Changes in immigration policies and enforcement practices, possible undoing of Obamacare, as well as growing anti-immigration sentiments will likely exacerbate health disparities experienced by Latino immigrants over the next four years. President's Trump threat to defund Sanctuary Cities, like Philadelphia, can have profound effects on vulnerable communities and, especially, immigrant populations. The evolving socio-political climate is expected to translate into an increase in prevalence and less access to services,  especially for stigmatizing conditions and behaviors such as HIV/STIs, substance use, mental health, and violence victimization. Research to identify effective strategies for their prevention and treatment and to promote resilience among immigrant populations is timely and more relevant than ever.

Project CRiSOL focuses on a syndemic of health factors, instead of just one factor since the syndemics conceptual framework is gaining ground in public health and health care delivery. Syndemics theory compels us to try to understand how different health problems "interact synergistically" within a community, identify risk and protective factors that connect them, and develop integrated interventions to simultaneously address these concomitant health problems and their shared social determinants. As stated in the Lancet's Syndemic Series, a syndemics approach is a notable conceptual instrument in population health science and can be used to tackle health inequities in a comprehensive and effective way.

A syndemic model of substance use, HIV/AIDS, violence, and mental health (SAVAME) has been established among Latinos.  The adverse interaction of the SAVAME factors is well documented. Limited access to HIV treatment augments the physical and mental health impact and perpetuates transmission of HIV. Substance abuse increases the risk for HIV/AIDS,  poor mental health,  and violence victimization.  Mental health conditions can lead to drug addiction,  violence,  and HIV risk behavior.  IPV is a risk factor for HIV infection and a cause of stress and trauma.  However, despite evidence of these synergistic interactions, these problems continue to be tackled separately.

Evidence on effective strategies to curb the SAVAME syndemic afflicting Latino immigrants is sorely needed. Peer- driven interventions have been found to increase access to health care and contribute to reduce health disparities among hard-to-reach, marginalized communities.  A particularly successful peer-driven approach is the Popular Opinion Leader (POL) model. Based on the Diffusion of Innovation theory,  POL programs recruit and train influential community members to serve as early adopters of new behavioral norms (e.g. risk reduction practices, utilization of prevention and treatment services, etc.), helping disseminate these new norms among community members in their social networks.  POL approaches have been applied with success to address HIV risk,  but without enough attention to the syndemic relation with substance use, poor mental health, and violence victimization. 

A community resilience framework offers an innovative approach to address the SAVAME syndemic among Latinos. Resilience theory is a strengths-based approach to enable individuals and communities to successfully overcome adversity and trauma. Community resilience can be fostered by engaging and empowering members of disadvantaged and underrepresented communities in health promotive activities and establishing formal and informal ties between these individuals and the available assets and resources in the community. Additional information of change within their own social networks could increase the capacity of this community to respond to the SAVAME syndemic in more effective and sustainable ways.

The Philadelphia AIDS Consortium (TPAC) has experience using a POL model for HIV prevention and has begun to offer Resilience Training to providers and community members in Philadelphia. In this pilot study, we have adapted TPAC's existing POL program^68 to target the four SAVAME syndemic factors, not just HIV risk, in the Latino immigrant community. Elements of other evidence-based Latino interventions have been incorporated to address the mental health, domestic violence and substance use components. In addition to this new syndemic approach, the POL program will be enhanced with elements from TPAC's Resilience Training program. This enhancement recognizes that peers often face the same challenging circumstances as the individuals they are trying to help and these challenges reduce their ability to serve as influential change agents. The Resilience Training will empower POLs to more aptly overcome adversity, so they can also better serve their communities. Resilience training will bolster the impact and sustainability of the POL program. To our knowledge, no intervention has incorporated syndemics, POL, and resilience theory to address the SAVAME syndemic in Latinos.

This study has two components that will help fill needed research gaps. The first component will be the adapted POL training program, where Latino immigrant leaders (hereafter referred to as POLs) will be trained and equipped with various skills and knowledge to help peers in their communities. Throughout this research proposal, this component of the research study will be designated as: "POL program" or "POL Training Program".

Once POLs are trained, they will be surveying their peers in the community (hereafter referred to as "community contacts") about their experience with the POL (e.g. satisfaction, intentions to follow-through with referrals). Community contacts are individuals within the POLs social network who are potentially at risk for or affected by the SAVAME factors. POLs will also offer community contacts the opportunity to take a survey about their experiences with the SAVAME syndemic. This survey hopes to gather preliminary data about the extent to which SAVAME conditions impact Latino immigrants in Philadelphia. Any section of this IRB proposal discussing the community contacts survey component of the research study will be designated "Community Contacts". These layers of participation are standard in peer-driven research projects, where peers have often been trained to serve as intervention delivery agents and to collect data from community members. Peer researchers have an important role community-based participatory approaches to researcher.

#### 5) Inclusion and Exclusion Criteria:

Popular Opinion Leaders (POLs)

This is a community-academic collaborative study. Our community partners will select POLs through their own contacts in the community, aided by intervention advertisement flyers. Applying the POL model, community partners will identify men and women who are most popular, well-liked, and trusted by others in the Latino immigrant community. Specific inclusion criteria are listed below:

- Over 18 years of age
- Bilingual in English and Spanish
- Member of Latino immigrant community (self-identified)
- Experience or connection with the SAVAME factors (e.g. they or someone close to them have been affected at some point by one or more of the syndemic factors).
- Self-describes as "people's person" and comfortable talking to others
- A significant social network in Philadelphia (self-report)
- Perceived as trustworthy and influential (by self and by community partners)
- Highly motivated to serve as agents of change in their community (self-report)
- Have time for training and project-related activities (self-report)
- Plans to stay in Philly for the foreseeable future (self-report)

Our team will strive to recruit a diverse group of POLs, in terms of gender, country of origin, sexual orientation, and area of residence, so their networks can reach a large and diverse share of the Latino immigrant population in Philadelphia.

Eligibility to be a POL will be determined through interviews with co-investigators and community partners. Final selection of POLs will be at the discretion of co-investigators and community partners after the interview process.

For the second year, POLs that participated during the first year will be invited to participate. Additionally, we will recruit new leaders using flyers.

#### Community contacts:

As interventionists and data collectors, POLs will interact (i.e. face to face, social media, by phone) with community contacts within their own social networks during POL outreach. They will document the reach of the intervention using iPads provided by our project and equipped with the Qualtrics survey software offline application or using a link on their phones.

Every time they interact with a community contact as part of the CRiSOL intervention, they will fill out a brief questionnaire (i.e. "POL Activity Log Survey"). Post interaction with POL, POLs will go through a brief verbal consent process and ask community members to complete a brief anonymous 2-minute "Satisfaction Survey.", followed by basic demographic characteristics to understand the population they are reaching. For a clearer description of the process, see the study timeline in the next section. If the contact was not made face to face, the POL will ask the community member to complete the survey through an online anonymous survey.

Inclusion criteria for the community interaction is as follows:

• 18 or older

- Bilingual in English or Spanish
- The POL had a conversation with them or provided services to them as part of the CRISOL intervention.

We will use a shortened version of the consent form considering the information to be collected is not sensitive and consisting only of satisfaction items and demographics. Also, please, note that the surveys will not contain any contact information.

After completion of this survey, the POL will invite the community member to participate in a more in-depth 20-minute survey that will be managed by our staff. If the participant accepts, the POL will collect a phone/email so our staff can send the link for the survey. Additionally, participants will be invited to complete a follow-up survey 3 months after the first survey.

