## 7) Study Endpoints

The primary endpoint of this study is to be able to assess the feasibility, acceptability, and efficacy of a peer-driven intervention to address the factors that contribute to this syndemic, increase access to SAVAME and COVID-19 prevention and treatment services, and reduce the prevalence and impact of the syndemic conditions and COVID-19 on the Latino immigrant community in Philadelphia.

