After 1 month of the implementation period (Community experience phase), the research team will conduct a semi-structured interview to gather opinions and overall satisfaction with the training, suggestions for amendments to the training in the future and their experience during the first month of community outreach. At the end of the 8-month implementation period (community experience phase), the research team will conduct semi-structured qualitative interviews with POLs, regardless of their continuation or level of activity. These interviews will

be conducted by trained project staff at TPAC offices. Questions for the exit interview will focus on the self-reported impact the training and application of CRISOL program had on POLs, including their assessment of the level, relevance, and quality of knowledge and skills acquired; impact on self-confidence, resilience, social capital, their role in the community, and future professional and personal plans. Interview guides will also cover challenges to serving as a POL, barriers and facilitators for their role, suggestions for ongoing support system, and ideas to maximize the impact of CRISOL on the community. This information will guide future improvements of the intervention.

POLs will document their activity in the community on the "POL Activity Log Survey" using iPads furnished with an offline Qualtrics® survey. POLs will log every interaction with community contacts and indicate the date, time, and place of the contact. POLs will also document their response to the issues discussed with the community contact which may include modeling of positive social norms, delivery of risk/harm reduction counseling, communication of health messages, linkage to resources, and navigation services to reduce SAVAME risk and impact. Collectively, we expect POLs will reach and register approximately 720 community contacts.

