#### Community contacts:

Post interaction with POLs, community members will complete a brief anonymous "Satisfaction Survey" based on their interaction with the POL, in addition to basic sociodemographic

characteristics. Community members will be provided with the informed consent script and must agree to participate before beginning the survey. The CRiSOL survey would be self-administered when the POLs and community contacts meet face-to-face, or administered by the POLs when interactions are made via phone or other media. The latter situation will be the case when social distancing measures are in place due to the coronavirus. The survey relies on Qualtrics®.

Note that by closing the survey, the answers of the individual cannot be accessed anymore except by the research team and no names or identifying information is included in the survey. A small incentive (i.e. a tote bag with the logo of the project) will be given to participants for their time when interactions are done face to face. This will not be possible when interactions are not face to face, such as during the coronavirus crisis.

For this second year, the study will be similar. Community members will complete an anonymous brief "satisfaction survey" after giving verbal consent (use of short consent version). Additionally, for this second year we are adding a new survey. POLs will invite community members to participate and collect phone numbers of the ones that agree. The research team will contact the community members that expressed interest, provide with a copy of the verbal consent and provide a link for them to take the survey. This survey will not collect any personal data. 300 community contacts will be invited to complete a follow-up survey 3 months after the completion of the first survey. The personal information needed to contact participants (i.e. phone number and first name) will be stored in a password-protected document.

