#### Community contacts:

As described above, after graduation, POLs will document their activity in the community using iPads furnished with an offline Qualtrics® survey. POLs will log every community contact they complete and indicate the date, time, and place of the contact ("POL Activity Log Survey"). For each community contact, POLs will document their community contacts' responses to the issues identified, which may include modeling of positive social norms, delivery of risk/harm reduction counseling, communication of health messages, linkage to resources, and navigation services to reduce SAVAME risk and impact. POLs will offer the community contact to take a satisfaction survey. The first survey ("Satisfaction Survey") can be self-administered by the community member and is designed to collect data on basic sociodemographic characteristics (e.g. age, gender, sexual orientation, race/ethnicity, etc.) and their satisfaction with the services received from the POL.

Collectively, we expect POLs will reach and register approximately 720 community contacts. These data will serve to establish the level of reach, implementation (feasibility), and maintenance of the intervention in the community and provide important community-level baseline data to describe the population reached by the POLs.

These quantitative data will be analyzed as follows: Parametric (one-way repeated measures ANOVA) or non-parametric tests (Friedman's test, general estimated equations), depending on

the level of measurement and observed distribution of the information. Analysis will be performed using IBM® SPSS® 22.0 and Stata 14.

All surveys offered as part of data collection on the community contact section of this protocol will be collected with and stored in Qualtrics®.

For the second year, we expect to follow same procedures as prior year. Additionally, we will be inviting community members to participate in an additional survey that measures risk behaviors and protective factors for SAVAME and COVID-19, as well as sociodemographic characteristics. After 3 months, those that expressed interest and gave consent will be contacted to complete a follow-up survey. These surveys will be collected and stored using Qualtrics ®.

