#### Community contacts:

The satisfaction community survey will be offered to all community members who the POLs interact with. Community contacts will also benefit from the informal support and resource referrals that POLs offer.

To incentivize their participation, community contacts will be offered a small token of appreciation for their participation in the satisfaction survey. This token will be an item branded with the CRiSOL and/or Drexel logos, such as a tote bag.

The community contacts that agree to participate in the additional surveys (i.e. base and follow up) will receive a \$25 e-gift card.

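### The SAP labels the study pre-post, but the baseline survey is offered only after a CRiSOL contact, so the co-primary change omits whatever that contact has already done

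*Protocol*

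**What the plan says.** The SAP's design statement describes a single-arm, non-randomised, pre-post study. Both co-primary outcomes, a COVID-19 exposure-risk score and the number of people lacking access to care, are assessed at baseline and 3 months. The SAP's analysis paragraph gives their only tests: paired t-tests and tests of proportions for change between those two times. The SAP summary offers the surveys to the first 300 community contacts.

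Protocol Section 5 (Community contacts) sets out the steps. One criterion for the community interaction is "The POL had a conversation with them or provided services to them as part of the CRISOL intervention". A short satisfaction survey follows the interaction, and then: "After completion of this survey, the POL will invite the community member to participate in a more in-depth 20-minute survey". For those who accept, "the POL will collect a phone/email so our staff can send the link for the survey". Section 8 times the second measurement: "300 community contacts will be invited to complete a follow-up survey 3 months after the completion of the first survey". Section 10 describes the year-2 instrument as "an additional survey that measures risk behaviors and protective factors for SAVAME and COVID-19". Section 7 makes it part of the primary endpoint to "assess the feasibility, acceptability, and efficacy of a peer-driven intervention to address the factors that contribute to this syndemic".

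On dates, Section 8 states: "POLs will log every interaction with community contacts and indicate the date, time, and place of the contact".

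**The concern.** A reader takes baseline in a pre-post design to mean before the intervention. Here the intervention is the opinion leader's contact, which the SAP summary describes as counselling on COVID-19 and the SAVAME factors. Those are the subjects that the survey measures. If the first survey is answered after such a contact, the comparison starts partway through the exposure, at a point that may differ between respondents.

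The stake is interpretation. Efficacy is part of the primary endpoint, and this change is the only test planned for the co-primary outcomes. The pilot is also meant to inform an application for an effectiveness trial (Protocol Section 3, aim 3). A change measured from after first contact, but reported as before versus after, would misdescribe what was estimated.

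**Working it through.** The documents give no sample-size or power figure for the 300, so there is nothing to reproduce. The check is of order and timing.

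1. **Order.** Section 5 gives this sequence: interaction, satisfaction survey, invitation to the 20-minute survey, collection of a phone number or email, link from staff. The invitation follows the satisfaction survey, which follows the interaction. The first survey therefore comes after at least one contact.

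2. **Other places.** Section 8 (Community contacts, second year) repeats the hand-over to staff but does not say that the new survey follows the satisfaction survey. The SAP's phrase about the first 300 contacts fits the Section 5 order but does not prove it, because Section 4 defines contacts as members of the leader's network. Section 14 mentions the two surveys only in connection with the gift card and says nothing on order. No section describes a measurement before contact. The order thus rests on Section 5, and nothing contradicts it.

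3. **Timing.** Let first contact be at time 0 and the first survey at time L. No section sets L. The year-2 calendar in Section 6 has a row for the baseline survey, but a calendar row cannot fix an interval for each person. Follow-up is timed from the first survey, so it falls at L + 3 months after contact.

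4. **What is tested.** Let Y(pre) be the value before contact. Define
   - D = Y(L + 3 months) − Y(pre), the change from before contact to follow-up;
   - E = Y(L) − Y(pre), the part already present at the first survey.

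   Tested change = Y(L + 3 months) − Y(L) = D − E. It equals D only if E = 0.

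5. **Direction.**
   - If E is an early favourable effect in the same direction as D, the tested change understates D.
   - If counselling makes people report more risk at first, E has the opposite sign and the tested change overstates the improvement.
   - If E is only a shift in reporting that persists unchanged to follow-up, it is in both surveys and cancels. The tested change is then the cleaner measure of behaviour.

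   The documents do not give the items, their recall periods or L, so none of these can be chosen over the others.

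6. **Which outcome.** The behaviour score (masks, hand washing, distancing) can move soon after counselling. Access to care is less exposed, since the effects of a referral take longer and would mostly fall between the two surveys.

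7. **Can L be recovered?** Section 8 has leaders log the date of each contact. Year 2 uses a separate COVID activity log whose fields are not listed, but Section 10 expects year-1 procedures to continue, so the date is probably planned. No section links a log entry to a survey respondent. Contact details are stored apart from survey data under unique identifiers (Section 13) and are exempt from the three-year retention rule (Section 10). The SAP does not mention the interval.

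**The case against.** The best case for the plan has four parts.

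- **Outreach is not one event.** It runs for 9 months in year 2, leaders log each interaction, and Section 27 says they work with people they already meet day to day. A survey near the first logged contact may still precede most of the exposure. This stands as a limit: the survey can be a baseline for later contacts, though not for the first, and repeat contact is not guaranteed for any respondent. Returning year-1 leaders may also have reached some respondents before, so even the first year-2 contact may not be the first exposure.
- **The SAP does not call the change an intervention effect.** It speaks of change from baseline and states that the study is single-arm and non-randomised. That is true of the analysis paragraph. But the pre-post label, together with efficacy in the primary endpoint, invites the reading, and nothing in the SAP guards against it.
- **The items may ask about a period before the contact.** If so, the label may be largely sound. Neither document gives the recall window.
- **No harm is shown.** This also stands. A reader might infer that the result is biased towards no change, or that the study loses power by a calculable amount. The documents support neither: they give no effect size, no standard deviation and no contact-to-survey delay, and the sign of E is open.

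A reader might also infer that year-2 contact dates will not be collected. Section 10 points the other way. What is missing is the link to the survey and the plan to report it.

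**Conclusion.** The point holds as one of description and reporting. Under Section 5, all 300 planned baseline surveys follow a CRiSOL contact at an interval that is neither set nor planned to be reported, and the only co-primary test starts from that survey. The tested change is D − E and leaves out any effect or reporting shift of the first contact that is already present. Its size and direction are not determinable from the documents, and no bias is demonstrated.

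The conclusion assumes that the Section 5 order applies to the year-2 survey, as its wording indicates and no other section disputes, and that the items do not refer to a pre-contact period. The absence of a comparator is a separate limit that the change below does not touch. It is still worth making the change before analysis: following the SAP as written would attach a pre-intervention starting point to an estimate that does not have one.

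**What to change.** **(a) SAP wording.** Describe the co-primary estimate as change from after the first CRiSOL contact to 3 months after the first survey, and state that it is not interpreted as before versus after intervention. The exception is if the co-primary items refer to a period before the contact. In that case, state the recall window used at both surveys.

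**(b) One linked date.** Carry the contact date that the activity log is expected to record into the survey dataset by unique identifier, before contact details are discarded. The satisfaction survey is anonymous and cannot serve as the link. A practical place to note the date is where the leader takes the phone number or email. Report the distribution of the contact-to-survey interval and, where the log can be linked, the number of contacts before the first survey.

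Any look at results by interval should be labelled descriptive. Respondents choose when to answer the link, so prompt and late responders may differ for other reasons. Such a look cannot recover E and is not a correction.

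**Cost.** SAP text, one linked field and a small IRB modification, with no extra participants. Moving the survey ahead of counselling is not needed for this fix; it would change the outreach workflow and might reduce uptake.
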